15.0 APPENDIX

15.1 Data derivation and analysis rules

The purpose of this section is to give technical details for the implementation of the SAP.

15.1.1 General specifications

15.1.1.1 Visit windows

The exact times at which IMP administration and mangoral-enhanced MRI are performed are defined in Section 5.1.5 of the protocol.

15.1.2 Disposition

All presentations for patient disposition will be done overall.

15.1.2.1 Patient discontinuation

Reasons for patient discontinuation as specified in the End-of- study page of the CRF will be used.

15.1.3 Demographics and other baseline characteristics

15.1.3.1 Patient demographics

Age as collected in CRF demographics form will be used.

15.1.3.2 Prior and concomitant medication

Prior and concomitant medication is collected as of enrollment in the CRF and described like that in the study protocol. For the analysis, the definition as described in the following is used.

The following rules are used to define the categories “prior” and “concomitant” medication.

Pre-requisite is a complete date/time of IMP administration (entered or imputed).

Stop of medication Date/time	Condition	Category
Complete date/time is available	Stop date/time is earlier than date/time of first dose of IMP.	Prior
Missing month	Year of stop date is earlier than year of first dose of IMP.	Prior
Missing day	Month/year of stop date are earlier than month/year of first dose of IMP.	Prior
Missing hours	Day/month/year of stop date are earlier than day/month/year of first dose of IMP.	Prior
Missing minutes	Day/month/year/hours of stop date/time are earlier than day/month/year/hours of first dose of IMP.	Prior
Otherwise		Concomitant

Medication ticked in the CRF as “continuing” will be classified as concomitant.

15.1.4 Safety analysis

15.1.4.1 Adverse events

The result of all imputation strategies (e.g., incomplete start dates of adverse events) and new derived information must be stored in the corresponding analysis dataset.

Handling of missing date information

The term missing date/time refers to a completely missing date/time or to an incomplete date/time where parts are not available, e.g., missing hours.

Missing start and end date/times will be imputed conservatively, i.e., missing values will be imputed in such a way that the duration of the adverse event is considered with the longest possible duration.

Imputation

I1: Impute AE start date with:

A replacement of missing year for AE start information is not foreseen. If needed, this will be considered on a case-by-case decision which must be documented.

a) If year of AE is the same as year of treatment then set start date to the date of treatment, otherwise use first calendar day and/or first calendar month.

Imputation will be done based on the available partial information starting with month and then day:

Missing date	Date of treatment	Imputed date
2014-Mar	2014-Mar-XX	2014-Mar-XX
2014-Mar	Not 2014-Mar	2014-Mar-01
2014	2014-XXX-XX	2014-XXX-XX
2014	Not 2014	2014-Jan-01

b) First hour and/or first minute.

Imputation will be done based on the available partial information starting with hour and then minutes:

Missing time	Date time of treatment	Imputed time
11:--	11:XX	11:XX
11:--	Not 11	11:00
--:--	Known	Time of treatment
--:--	Unknown	00:00

I2: Impute AE stop date with:

a) Last calendar day and/or calendar last month.

Imputation will be done based on the available partial information starting with month and then day. The respective last month and day will be chosen for imputation:

Missing date	Imputed data
2014-Mar	2014-Mar-31
2014	2014-Dec-31

For February, leap years must to be taken into account when calculating the last day in February.

b) Last hour and/or last minute.

Imputation will be done based on the available partial information starting with hour and then minutes. The respective last hour of a day and last minute will be chosen for imputation. "23:59" will be considered as the last hour/last minute per day.

Missing time	Imputed time
11:--	11:59
--:--	23:59

List of deaths

Death will be identified by the outcome of adverse event if the outcome equals "fatal" or reason for end of study is "dead".

Patient experiencing a non-serious adverse event

All patients who had at least 1 non-serious AE will be taken into account regardless of the experience of a serious AE.

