11.2 Definitions and Derived Variables

11.2.1 Definitions

For the statistical analysis, the different MRI methods will be denoted according to the following table.

Table 6 Labeling of MRI methods

MR1 Method	Short label (for tables etc.)
unenhanced MRI	UnMRI
mangoral-enhanced MRI	MeMRI
combined MRI (mangoral-enhanced MRI plus unenhanced MRI)	CMRI

In the following table, the definitions and calculation of derived variables are summarized.

Table 7 Further definitions

Variable / Term	Definition / Way of calculation
Baseline	The last assessment made before the administration of IMP will be used as baseline.

Variable / Term	Definition / Way of calculation
Change from baseline at visit	The difference between a value at time point and the value at baseline
Study day	
The day of IMP is defined as study Day 1.
 
Calculate the study day according to the following rules:
 
If date < date of IMP, then study day = date of IMP - Date.
 
If date ≥ date of IMP, then study day = Date – date of IMP + 1.

Age [years]	Year of informed consent – Year of birth
Age categories	
≥ 18 - < 65 years
 
≥ 65 - < 75 years
 
≥ 75 years

Body Mass Index (BMI)	$\text{BMI [kg/m}^2\text{]} = \frac{\text{Weight [kg]}}{\text{Height [m}^2\text{]}}$
Study duration [days]	Date of completion/discontinuation – date of informed consent + 1
Prior medication	
Any medication taken and stopped before the date of administration of mangoral.
 
If the end date of prior medication is missing or partial see Section 15.1.3.2.

Concomitant medication	
Any medication taken prior to the administration of mangoral and continuing after treatment or started after the date of administration of mangoral.
 
If the end date of concomitant medication is missing or partial see Section 15.1.3.2.

Adverse events	All untoward medical occurrences after signing the informed consent. These can be adverse events either prior to treatment or after treatment as collected in the CRF.
Time to onset of adverse events	Time to onset of adverse events will be calculated based on the administration start date time of IMP based on the imputed value for adverse event start date/time.

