Duration of adverse events	
Duration of adverse events will be calculated based on the imputed values for adverse event start date/time and stop date/time.
 
If the duration of the adverse event could not be calculated due to unknown date information, the following assessment to categories will be used:
 
 If the adverse event is marked as "ongoing" in the CRF or the end date is missing, the duration will be categorized as "ongoing". Otherwise, the duration category will be set to "missing".
Flagging of laboratory parameters	Continuous parameters will be classified as low , normal , or high based on reference (normal) ranges. In addition, laboratory parameters are flagged also according to CTCAE grading (G) as G1, G2, G3, or G4
Reproducibility	A consistency of results obtained when the same imaging is performed at short intervals on the same patients using different methods and by different readers.
QTcB interval (msec)	$\text{QTcB interval (msec)} = \frac{\text{QT interval (msec)}}{(\text{RR interval (sec)})^{1/2}}$

Variable / Term	Definition / Way of calculation
QTcF interval (msec)	$\text{QTcF interval (msec)} = \frac{\text{QT interval (msec)}}{(\text{RR interval (sec)})^{1/3}}$

The raw datasets will be in the Study Data Tabulation Model (SDTM) and the analysis datasets will be in the Analysis Data Model (ADaM), where ADaM datasets are derived from SDTM datasets. Throughout the entire study only one CDISC version will be used, there will be no change even if a higher version is available.

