13.8.1 Adverse Events

Safety analysis will include the investigation of adverse events (AEs), serious adverse events (SAEs), AEs related to IMP and SAEs related to IMP.

The following events shall be reported always as SAEs:

- seizure
- stroke
- cerebral venous thrombosis
- QTcF or QTcB greater than 480 msec
- OTcF or QTcB increase of 60 msec over baseline

For all AEs, a summary containing the following counts of patients, percentages of patients and number of events will be presented by pre and post dose (per CRF):

- Number of AEs;
- Number of related AEs;
- Number of AEs leading to study discontinuation (AE caused the patient to be discontinued from the study);
- Number of related AEs leading to study discontinuation;
- Number of SAEs;
- Number of related SAEs;
- Number of grade 3 or greater AEs;
- Number of grade 3 or greater related AEs;
- Number of AEs recovered;
- Number of AEs recovering;
- Number of AEs with outcome of death.

Further, all AEs, SAEs, AEs related to IMP and non-serious AEs will be summarized in a frequency table by MedDRA system organ class (SOC) and preferred term (PT), presented by pre and post dose (per CRF). The version of the utilized dictionary will be presented as part of the provided tables and listings. Tables will be sorted by decreasing frequency for SOC then PT within SOC using the overall column.

A summary of AEs by SOC, PT and maximum CTCAE grade will be presented.

Additionally, a summary of frequent post dose AEs (experienced by $\geq 5\%$ of dosed patients) by PT will be displayed summarizing time to event (hours) and duration of event (hours) with summary statistics. For handling partial date/times refer to [Section 15.1.4.1](#). If an AE has no end date (ongoing at end of study) this will not be included in the analysis of duration of event.

All AEs, SAEs (other than death) and AEs leading to study discontinuation will be listed. In addition, a listing for AEs leading to death will be presented. Listings of AEs leading to death and SAEs (other than death) will be presented on screened patients and other AE listings will be presented on enrolled patients.

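### AE onset imputation (SAP 15.1.4.1, I1 b) gives a missing onset time the dosing clock time on any date, so AEs after the dosing day start late and can have negative durations

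*SAP*

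**What the plan says.** SAP 15.1.4.1 sets the principle for missing AE dates and times: "missing values will be imputed in such a way that the duration of the adverse event is considered with the longest possible duration". Rule I1 then handles the start in two steps.

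- **Date (I1 a).** The sentence reads: "If year of AE is the same as year of treatment then set start date to the date of treatment". The table below it is narrower. Where the month is known, it uses the treatment date only if treatment fell in that month, and otherwise the first of the recorded month.
- **Time (I1 b).** The step is headed "First hour and/or first minute". In its table, a fully missing time becomes the "time of treatment" whenever that is known, and 00:00 only when it is not. A known hour with missing minutes takes the dosing minute if the dosing hour is the same, and otherwise minute 00. No row mentions the date of the AE.

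Rule I2 moves a missing stop time to the end of the day and leaves a recorded stop as it is. Nothing prevents an imputed start from falling after a recorded stop.

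The imputed values are used. SAP 11.2.1 says: "Duration of adverse events will be calculated based on the imputed values for adverse event start date/time and stop date/time". For onset it says: "Time to onset of adverse events will be calculated based on the administration start date time of IMP", again with the imputed start. SAP 13.8.1 plans a table of post-dose AEs seen in at least 5% of dosed patients, "summarizing time to event (hours) and duration of event (hours) with summary statistics".

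**The concern.** The longest possible duration requires the earliest possible start. For a post-dose AE on the dosing day, that is the dosing time, and the table is right. For an AE on any later day, it is 00:00 of that day, and the table instead gives the hour at which the patient happened to be dosed. The rule therefore departs from both its principle and its heading, and it can produce a start later than a known stop.

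Later-day onsets are expected. Protocol 6.3.7 collects AEs to day 5 (±2), or to day 7 in the brain MRI subgroup. At stake is the planned summary of AE timing in hours. Protocol 1.1.4 describes the known reactions as mainly mild, transient gastrointestinal symptoms, and for short events a shift of several hours is large.

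In I1 a, sentence and table disagree when dosing falls in the same year as the AE but in another month. Two programmers could each follow the SAP and store different start dates.

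**Working it through.** The documents give no figure to reproduce. The check applies the rules literally to worked dates; all dosing times and dates below are assumptions.

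**Time rule, general form.** Let c be the dosing clock time in hours after midnight. Take an AE that starts k days after the dosing day (k ≥ 1) with its time fully missing.

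- Imputed start = AE date + c. Earliest possible start = AE date + 0. The difference is c.
- Imputed time to onset = 24k + c − c = 24k. Earliest possible = 24k − c. Every such AE therefore lands on an exact multiple of 24 h.
- Imputed duration = longest possible duration − c. It is negative when the recorded stop is on the start date, before c.

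**Worked cases**

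| Dose | AE start | Recorded stop | Imputed start | Duration by I1 b | Longest possible |
|---|---|---|---|---|---|
| 12:00 | next day, no time | same day 07:00 | 12:00 | 7 − 12 = −5 h | 7 h |
| 12:00 | next day, no time | following day 07:00 | 12:00 | 31 − 12 = 19 h | 31 h |
| 10 Mar 14:00 | 12 Mar, no time | 12 Mar 09:30 | 14:00 | 9.5 − 14 = −4.5 h | 9.5 h |
| 10 Mar 14:00 | 12 Mar, no time | 12 Mar 18:00 | 14:00 | 18 − 14 = 4.0 h | 18.0 h |
| 11:45 | later day, 11:-- | same day 11:30 | 11:45 | −15 min | 30 min |

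In the first case, time to onset is 24 h by the rule and 12 h at the earliest. If both times are missing, I2 sets the stop to 23:59. Duration is then positive but still short by c: with a 12:00 dose, 11 h 59 min instead of 23 h 59 min.

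**Range.** For dosing between 08:00 and 16:00 (assumed), the shift is 8 to 16 h per AE.

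**How often the sign flips, illustration only.** Assume onset uniform over the day, exponential duration with mean 4 h, and a recorded stop on the same, non-dosing day. Of such AEs with a missing onset time, 23%, 41% and 60% get a negative duration for dosing at 08:00, 12:00 and 16:00.

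**Date rule, sentence against table**

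- AE 2014-Mar, dosing 20 Apr 2014: the sentence gives 20 Apr, the table 1 Mar.
- AE 2014-Mar, dosing 27 Feb 2014: the sentence gives 27 Feb, the table 1 Mar. For this post-dose AE, the sentence moves the start earlier, out of the recorded month.
- Pre-dose event 2023-Mar, dosing 20 Apr 14:00, stop 25 Mar 12:00: the sentence gives a start 26 days 2 h after the stop, −626 h. The table date with the dosing time gives +574 h; with 00:00 it would be +588 h.
- Pre-dose event 2023-Mar, dosing 20 Mar 14:00, stop 10 Mar 12:00: sentence and table both give −242 h.

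For post-dose AEs, late starts and negative durations therefore come from the time rule. The date rule gives a start after the stop only for pre-dose events, and in the dosing month the table does so as well as the sentence.

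**The case against.** **Few AEs may be affected.** Protocol 6.3.7.2 asks for onset and end date and time for each AE, 9.2.3 allows no unanswered eCRF question, and 9.1 provides for validation checks and queries. A negative duration also needs a start after the dosing day, a missing onset time, and a recorded stop that same day before the dosing clock time. This stands: the rate is unknown. But the SAP itself provides for missing times, Visits 4 and 5 may be remote for patients outside the PK subgroup, and the shortening does not need the narrow combination.

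**Midnight is not nearer the truth.** The shift is measured from the earliest possible onset, not the true one. If onsets were uniform over the day, 00:00 would be early by 12 h on average, and a 12:00 imputation would be right on average. This also stands. The documents do not show that the rule biases the true time course. They show that it breaks the plan's own principle and permits impossible values.

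**The column header refers to the date and time of treatment, so a date match may be implied.** This does not hold. For a fully missing time, the only entries are whether the dosing time is known or unknown, so an AE on another date would then have no rule.

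**The date conflict resolves itself.** The SAP adds that imputation works from the known parts of the date, which favours the table. That reading is reasonable, but the sentence still says something else.

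A reader might infer that the date conflict also distorts the reported time and duration table. It does not give late or negative values there: that table covers post-dose AEs only, and for these the sentence can only move a start earlier. A reader might also infer that the main tolerability results are at risk. The main tables in SAP 13.8.1 are counts and frequencies, split into pre- and post-dose by the CRF, so imputed dates do not reclassify events. The time and duration table is an addition to them.

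**Conclusion.** The point holds for the time rule. Read as written, I1 b contradicts the principle and heading of its own section. For each post-dose AE that starts after the dosing day with a fully missing time, onset is later than the earliest possible time by the dosing clock time, and duration is shorter by the same amount. Where only the minutes are missing and the hour equals the dosing hour, the shift is the dosing minute, under one hour.

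The size is known per event only, and rests on assumed dosing times. The consequence is confined to a supplementary descriptive table of frequent post-dose AEs. The contradiction in I1 a is a separate matter of stored dates. The correction is worth making because the present rule can print negative durations, but it does not bear on the trial's conclusions.

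**What to change.** In SAP 15.1.4.1:

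1. **I1 b.** Use the dosing time (or dosing minute) only when the AE start date equals the dosing date and the event is post-dose per CRF. Otherwise use 00:00, or minute 00 of a known hour.
2. **I1 a.** Reword the sentence to match its table: use the dosing date when every known part of the AE date agrees with it, and otherwise the first possible day. Apply the dosing-date replacement only to events marked post-dose on the CRF.
3. **Both.** Do not allow an imputed start later than a recorded stop.

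With the first change, the next-day AE that stopped at 07:00 lasts 7 h, and the two 12 March cases last 9.5 h and 18.0 h. The second and third remove the −626 h and −242 h results for pre-dose events. The cost is a few words in the appendix and simple conditions in the AE dataset program, with no new data and no burden on patients.

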#### **6.3.7.3 Follow-up of adverse events**

Each unresolved AE at the patients' individual study termination must be followed up until it subsides or until the cause is known or an adequate final assessment can be given. The maximum follow-up period will be 4 weeks after the patient's study termination. If after 4 weeks no final outcome can be acquired, the outcome of the AE is 'unresolved'.

For all patients with clinically significant abnormal laboratory findings at 5 ( $\pm$  2) days post-dose compared to the baseline evaluation (within 24 hours prior to the administration of IMP), the laboratory test will be repeated to ensure the validity of the abnormal result. Confirmed abnormal values will be followed up until normalisation to baseline level or until there is no medical necessity for further blood tests in the investigator's opinion. Therefore, the patient might have to come to the site for one or more unscheduled follow-up visits.

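### The AE stop-date imputation has no upper limit, so an imputed stop can fall after death, last contact or the end of AE follow-up

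*SAP*

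**What the plan says.** SAP 15.1.4.1 states the aim of its date rules: "missing values will be imputed in such a way that the duration of the adverse event is considered with the longest possible duration". Rule I2 then fills a partial stop date with the "Last calendar day and/or calendar last month". It adds that "The respective last month and day will be chosen for imputation", and a missing time becomes the last minute of the day. The section mentions death only to build the list of deaths, not to limit a stop date. Rule I1, for onsets, does tie the imputed value to a known event: it uses the treatment date where the known parts of the date match.

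The imputed dates reach a reported table. SAP 11.2.1 says: "Duration of adverse events will be calculated based on the imputed values for adverse event start date/time and stop date/time". SAP 13.8.1 describes a table of post-dose AEs experienced by at least 5% of dosed patients, "summarizing time to event (hours) and duration of event (hours) with summary statistics". Events without any end date are left out: "If an AE has no end date (ongoing at end of study) this will not be included in the analysis of duration of event". Events with a partial end date stay in.

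Protocol 6.3.7 ends AE reporting at day 5 (±2), or around day 7 in the brain MRI subgroup, whose visit window is 7 (+2) days. For AEs unresolved at termination, Protocol 6.3.7.3 says: "The maximum follow-up period will be 4 weeks after the patient's study termination". Two groups can be followed longer: confirmed laboratory abnormalities (6.3.7.3) and SAEs related to the product or to trial procedures (6.3.7.4).

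**The concern.** A rule that aims for the longest possible duration should not return an impossible one. Without an upper limit, I2 can place the end of an event after the patient has died, after the last contact, or after follow-up for that event has closed. For an ordinary AE with no final outcome after four weeks, Protocol 6.3.7.3 has the outcome recorded as unresolved, so a resolution date months later does not fit the protocol's own recording rule.

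At stake is how the duration of the commoner reactions is described. With 80 dosed patients, the enrolment figure in SAP 9.3, the 5% threshold is 0.05 × 80 = 4 patients. In a row that small, one artefact can set the mean, SD and maximum.

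**Working it through.** **The rule itself.** Applying I2 reproduces the SAP's own examples: 2014-Mar becomes 31 March 2014, and 2014 becomes 31 December 2014.

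**How long general AE follow-up can last, counted from dosing** (termination day plus 28 days, × 24):
- day 5: 33 × 24 = 792 h
- day 7: 35 × 24 = 840 h
- day 9 (late edge of the brain MRI window): 37 × 24 = 888 h

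Earlier termination lowers these figures.

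**One worked event** (illustrative). Dose and onset are on 2 March at 14:00.
- Stop entered as March: to 31 March 23:59 is 29 days and just under 10 h, so 29 × 24 + 10 ≈ 706 h.
- Stop entered as the year only: to 31 December 23:59 is 304 days and just under 10 h, so 304 × 24 + 10 ≈ 7,306 h.

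The year-only value exceeds 888 h by a factor of about 8 (7,306 / 888). The month-only value is inside 792 h. It becomes impossible if something more is known, for example that the event had resolved by Visit 6 on 7 March at 14:00. The ceiling is then 5 × 24 = 120 h, for either form of partial date.

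**Effect on a four-event row.** Assume three other events of 10 h each. The mean is (duration + 30) / 4. With three equal values, the SD is (duration − 10) / 2.

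| Stop entered | Limit applied | Duration = maximum (h) | Mean (h) | SD (h) | Median (h) |
|---|---|---|---|---|---|
| Month only | none | 706 | 184 | 348 | 10 |
| Year only | none | 7,306 | 1,834 | 3,648 | 10 |
| Either | resolved by Visit 6 | 120 | 37.5 | 55 | 10 |
| Year only, resolution visit not known | 840 h | 840 | 217.5 | 415 | 10 |

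**Over all dosing dates.** Assumptions: calendar year 2022, dose and onset at 09:00, stop date reduced to month or year.

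| True duration | Stop entered | Range (h) | Median (h) | Share above 792 h | Share above 888 h |
|---|---|---|---|---|---|
| 24 h | month only | 39–759 | 399 | 0% | 0% |
| 120 h | month only | 135–855 | 495 | 8% | 0% |
| 24 h | year only | 39–8,775 | 4,407 | 91% | 90% |
| 120 h | year only | 135–8,871 | 4,503 | 92% | 91% |

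Month-only dates pass the limit by a wide margin only when the true stop falls in a later month. With follow-up to 35 days the worst case is about 1,575 h (onset 25 January, stop entered as March).

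**What each limit achieves** (true duration 24 h). A limit at 840 h takes the year-only median from 4,407 h to 840 h and the maximum from 8,775 h to 840 h. It leaves month-only values unchanged (median 399 h, maximum 759 h). A limit at the day-5 visit, where the event is known to have resolved by then, brings the median to 120 h for both.

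**The case against.** The conservative direction is declared and deliberate, and partial stop dates should be rare. Protocol 6.3.7.2 requires an end date and time, contacts fall at 24 h, 48 h and day 5, Protocol 9.2.3 asks for prompt and complete eCRF entry, and Protocol 9.1 provides plausibility checks and queries. A year-only stop in a study this short would be unusual. The table also reports medians and quartiles, and the median in the example stays at 10 h. All AEs are listed and imputed values are stored in the analysis dataset, so an odd duration can be traced. All of this stands, and it keeps the point small. It does not make a stop date after death or last contact a possible one.

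A reader might infer that follow-up rules out any imputed duration of hundreds of hours. The documents do not support that. An AE unresolved at termination may be followed to 792–888 h, and most month-only imputations lie within that range. The 706 h in the example is impossible only because that event is known to have resolved by Visit 6.

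A reader might also treat 840 h or 888 h as a ceiling for every event. It is not: confirmed laboratory abnormalities and related SAEs may be followed longer, and a blanket four-week limit could cut off genuine follow-up.

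Finally, SAP 11.1.1 says that missing data are not imputed. That does not cancel I2, because 11.1.2 sends partial AE dates to 15.1.4.1.

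**Conclusion.** The point holds as a minor gap in a data-handling rule. I2 has no upper limit and no other section supplies one, so it can return durations that contradict its own stated aim. Year-only stops are the main fault: on the assumptions above, about 90% of dosing dates give more than 888 h. Month-only stops are at fault only in the three situations named: earlier death or last contact, known resolution by a given visit, or a stop month that runs past follow-up.

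The reach is one descriptive safety table, through the mean, SD and maximum and possibly the upper quartile. AE counts, grades, relatedness and the primary endpoint are unaffected. The documents do not say how many stop dates are partial, so the actual shift in that table cannot be computed. The four-event row shows how sensitive the statistics are; it is not a forecast.

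**What to change.** Add one sentence to I2: the imputed stop is the earliest of
- the calendar end now specified,
- the date of death,
- the date of last contact, and
- the end of the follow-up that applies to that event. For ordinary AEs this is study termination plus 4 weeks; for laboratory abnormalities and related SAEs followed longer it is the actual last contact.

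Where the data show the event recorded as resolved at a visit, that visit date is a further limit. Flag imputed durations in the AE listing.

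The conservative intent is kept, because the longest duration that could have occurred is still used. The cost is a sentence in the SAP and a small change to dataset code. The visit-based limit may need more: the AE items in Protocol 6.3.7.2 include the outcome but no date on which it was recorded, so the study team should first check whether that date can be recovered from the data.
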